#### 9.5.1. Bioanalysis

Samples will be analyzed at a laboratory approved by the sponsor and stored at a facility designated by the sponsor.

Concentrations of lasmiditan and metabolites M7, M8, (S,R)-M18, and (S,S)-M18 will be assayed using a validated liquid chromatography with tandem mass spectrometry method. Analyses of samples collected from placebo-treated subjects are not planned.

Bioanalytical samples collected to measure investigational product concentrations will be retained for a maximum of 2 years following last subject visit for the study. During this time, samples remaining after the bioanalyses may be used for exploratory analyses such as metabolism and/or protein binding work.

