7. SAMPLE SIZE JUSTIFICATION

The sample size is customary for Phase 1 studies evaluating safety and PK, and is not powered on the basis of statistical hypothesis testing.

Subjects who are randomized but not administered treatment may be replaced to ensure that approximately 14 Japanese and 8 Caucasian subjects (approximately 2 per treatment sequence) may complete the study.

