9.4.5 Electrocardiogram (ECG)

The ECG data will be obtained directly from the 12-lead ECG traces. These data include the PR and QT intervals, QRS duration and heart rate. In addition, QTcF (the QT interval corrected using Fridericia's formula) will be calculated as follows:

$$QTcF = \frac{QT}{\sqrt[3]{(60/HR)}}$$

The ECG data will be listed and summarized by population and treatment, together with changes from baseline, where baseline is defined as the mean of the average values of the triplicate assessments collected at -1 hour, -0.5 hours, and predose on Period 1. All other time points are considered as post baseline, including predose on Periods 2 and 3.

Figures of mean ECG data and mean changes from baseline will be presented by population and treatment. The frequency of subjects with a maximum increase from baseline in QTcF interval will be summarized by population and treatment according to the following categories: >30 ms and >60 ms. In addition, the frequency of subjects with QTcF postdose values, according to the following categories: >450 ms, >480 ms and >500 ms, will be summarized by population and treatment.

The relationship between concentrations of lasmiditan and changes from baseline QTcF (Δ QTcF) will be explored graphically, using different symbols and colours for each group. The comparisons to be explored are:

- Japanese vs Caucasian
- Japanese (Male vs Female)
- Caucasian (Male vs Female)

A linear mixed-effects model will be fitted with the change from baseline in QTcF (Δ QTcF) as the response, the time-matched concentration as a covariate, population or sex and time-matched concentration-by-population (or sex) as fixed effects for the population or sex analysis respectively, and subject as a random effect. Population and sex will be fitted as binary variables, as appropriate (0=Caucasian, 1=Japanese, 0=Male, 1=Female accordingly). The intercept, slope, and random effect covariance from the model along with their 90% CI will be reported. If the model fails to converge, alternative models will be tested. A scatter plot of Δ QTcF versus the concentrations with the fitted lines will also be plotted. Additional analysis may be performed, if deemed necessary.

Example SAS Code:

```
proc mixed data=ecg alpha=0.1;
  class usubjid effect;
  model chg_qtcf = conc + effect + conc*effect / alpha=0.1 cl solution
  residual ddfm=bw;
  random intercept conc / subject=usubjid type=un s;
run;
```

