where effect represents “population” for the comparison of Japanese versus Caucasian, and “sex” for the comparison of males versus females within each population.

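### SAP 9.4.5 takes between-within degrees of freedom for a model with subject-specific QTcF slopes, so the 90% CIs for the slope and its sex difference are somewhat too narrow if slopes vary materially between subjects

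*SAP*

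**What the plan says.** The fixed part of the model in SAP 9.4.5 is "model chg_qtcf = conc + effect + conc*effect / alpha=0.1 cl solution". The random part is "random intercept conc / subject=usubjid type=un s", so each subject has an intercept and a concentration slope of their own, with an unstructured covariance between the two. Degrees of freedom are set by "residual ddfm=bw". There is no REPEATED statement. The procedure call, "proc mixed data=ecg alpha=0.1", fixes the level at 90%.

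The text commits to reporting the result: "The intercept, slope, and random effect covariance from the model along with their 90% CI will be reported". The grouping factor is population "for the comparison of Japanese versus Caucasian, and “sex” for the comparison of males versus females within each population". That makes three models: all subjects by population, Japanese by sex, and Caucasian by sex.

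SAP section 7 plans that "approximately 14 Japanese and 8 Caucasian subjects (approximately 2 per treatment sequence) may complete the study". Randomization is stratified by sex with roughly equal numbers per cohort, so the Caucasian sex model compares about 4 men with 4 women. If the model does not converge, unspecified alternative models will be tried. Neither document says how many degrees of freedom any effect should receive.

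**The concern.** The between-within method splits the residual degrees of freedom into a between-subject and a within-subject part, and gives the within-subject part to any effect that changes within a subject. Concentration changes at every sample, so `conc` and `conc*effect` receive several hundred degrees of freedom and the interval multiplier is close to the normal value.

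That is reasonable if all subjects share one slope within a group. The SAP's own model says they need not. If slopes truly differ, more samples per subject sharpen each subject's slope but do not add subjects, and the precision of the mean slope is limited by their number. The t multiplier should then reflect about 6, 12 or 20 degrees of freedom.

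At stake is how firmly the QT slope, and its difference between men and women or between populations, appears to be known. Protocol 5.4 includes the 400 mg dose for QT assessment, and Protocol 10.3.1.2 leaves the detailed QT analysis to the SAP. This model is that analysis.

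**Working it through.** The plan states no degrees of freedom, power or precision for this model, so there is no figure to reproduce.

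**Step 1: observations.** Inputs are the sequence tables (SAP section 5) with 2 subjects per sequence, and the Schedule of Activities. ECG and PK samples coincide at 12 postdose times (1, 1.5, 2, 2.5, 3, 4, 6, 8, 12, 24, 36 and 48 h). The SAP counts predose in Periods 2 and 3 as post-baseline. This gives 12 pairs in Period 1 and 13 in each later period. Only active periods are counted, because Protocol 9.5.1 says "Analyses of samples collected from placebo-treated subjects are not planned".

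- Caucasian: 6 active subject-periods in Period 1 and 12 later, so 6×12 + 12×13 = 228.
- Japanese: 10 in Period 1 and 20 later, so 10×12 + 20×13 = 380.
- All: 228 + 380 = 608.

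**Step 2: degrees of freedom and multipliers.** With n subjects and N observations, between-subject df = n − 2 and within-subject df = N − n − 2. The last column is the chance that a t variable on n − 2 df falls within the within-subject multiplier.

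| Model | n | N | Within df | t(0.95) | n − 2 df | t(0.95) | Ratio | Coverage if n − 2 is right |
|---|---|---|---|---|---|---|---|---|
| Population | 22 | 608 | 584 | 1.647 | 20 | 1.725 | 0.955 | 0.885 |
| Japanese sex | 14 | 380 | 364 | 1.649 | 12 | 1.782 | 0.925 | 0.875 |
| Caucasian sex | 8 | 228 | 218 | 1.652 | 6 | 1.943 | 0.850 | 0.850 |

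Entering placebo periods at zero concentration raises the Caucasian count to 8×12 + 16×13 = 304 and the within df to 294. The multiplier becomes 1.650, practically the same.

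**Step 3: simulated coverage.** The SAP model was fitted by REML to data simulated on the planned sequences, 2,000 trials per cell (Monte Carlo SE about 0.007). The half-life of 4 h comes from Protocol 3.2. Assumed, because the documents give no values: intercept SD 6 ms, independent residuals with SD 7 ms, and slope SD in ms per concentration equal to the 200-mg Cmax. Each cell shows coverage of the nominal 90% CI for the reference slope / the slope difference.

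| Model | df rule | SD 2 | SD 5 | SD 10 |
|---|---|---|---|---|
| Caucasian sex | within | 0.906/0.904 | 0.854/0.850 | 0.855/0.858 |
| Caucasian sex | n − 2 | 0.956/0.944 | 0.902/0.904 | 0.901/0.906 |
| Japanese sex | within | 0.863/0.869 | 0.861/0.879 | 0.889/0.884 |
| Japanese sex | n − 2 | 0.894/0.893 | 0.880/0.904 | 0.909/0.906 |
| Population | within | 0.898/0.891 | 0.880/0.870 | 0.888/0.881 |
| Population | n − 2 | 0.914/0.910 | 0.894/0.884 | 0.901/0.894 |

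A separate run with the same intercept and residual SDs (1,000 trials per cell) gave, with within-subject df at slope SD 3 to 8, 0.84-0.88 for Caucasian sex and 0.84-0.86 for Japanese sex, and near 0.90 at SD 1. Another Caucasian-sex run (2,000 trials per cell) gave 0.90/0.90 at SD 1 and at SD 2, 0.87/0.87 at SD 3 and 0.87/0.85 at SD 5. The point at which the shortfall begins is not sharp: the Japanese sex model already shows it at SD 2 in the table.

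**The case against.** **The size rests on an unknown.** No slope SD appears in either document. At SD 1 coverage was near nominal, and at SD 2 the Caucasian sex model was nominal. Protocol 3.3 reports no significant QT prolongation at 100 or 400 mg, which neither establishes nor bounds variation between subjects. This objection stands, and the conclusion has to be conditional.

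**The analysis is exploratory.** The protocol speaks of exploring the relationship, the code is labelled an example, SAP 9.4.9 plans no inferential safety analysis, and the trial is not powered for testing. QTcF category counts are reported as well. All of this stands and lowers the priority. It does not make a stated 90% level accurate.

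**The software may already use between-subject df.** A reader may recall that between-within has an exception for an unstructured covariance, and conclude that nothing needs changing. As understood here, that exception concerns an unstructured REPEATED covariance with no RANDOM statement. The SAP code is the reverse: a RANDOM statement and no REPEATED. The documents cannot settle software behaviour; the DF column of the fixed-effects solution will. If it did show n − 2, the coverages in the n − 2 rows would apply and the change would matter little.

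**The remedy over-corrects in the smallest comparison.** This stands; the fix gives the size.

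**Stronger readings that the documents do not support.** A reader might infer that the intervals are too narrow whatever the data, or that the study's QT conclusions are unsafe. The first fails because coverage is near nominal when slopes hardly vary. The second fails because no margin, threshold or decision is tied to these limits.

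**Conclusion.** The concern holds conditionally. With the code as written, `conc` and `conc*effect` take about 218 (Caucasian), 364 (Japanese) or 584 (all) degrees of freedom, while the quantities of interest are informed by 8, 14 or 22 subjects. If the between-subject slope SD is about 3 ms or more per 200-mg Cmax, the nominal 90% CIs for the slope and its sex difference cover about 84-88%; the Japanese sex model at SD 10 came out slightly higher (0.889/0.884). With little slope variation coverage is near 90%. The population model is least affected, with a multiplier about 4.5% too small.

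This rests on the assumed variance components, on 2 completers per sequence, on active periods only, and on the general between-within rule applying to this code. A figure of roughly 300 df for the Caucasian model holds only if placebo periods are entered at zero concentration, which the SAP does not state. It is a low-priority correction to an exploratory analysis.

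**What to change.** In the SAP 9.4.5 code, replace `ddfm=bw` with `ddfm=kr`. State in the text that the 90% CIs for the fixed effects use Kenward-Roger degrees of freedom and standard errors. Apply this to the population model, both sex models, and any fallback model that keeps a random slope. When the program is first run, check the DF column of the fixed-effects solution.

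The edit is one option and one sentence. The statistical cost is wider intervals: in simulation by about 13-36% for Japanese sex and 23-43% for Caucasian sex. For the 4 v 4 Caucasian comparison Kenward-Roger is conservative, with about 92-98% coverage. These figures come from Kenward-Roger implementations written for the simulations and not from SAS, so they are approximate.

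A less conservative alternative for that comparison is a t multiplier on n − 2 subject-level df with the standard error unchanged. It widens the Caucasian sex interval by 1.943/1.652 − 1 = about 18% and the Japanese by 1.782/1.649 − 1 = about 8%, and covers about 89-95% for Caucasian sex. Whichever is chosen should be named before the data are analyzed.

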9.4.6 Hepatic Monitoring

If a subject experiences elevated alanine aminotransferase (ALT) $\geq 3 \times$ upper limit of normal (ULN), alkaline phosphatase (ALP) $\geq 2 \times$ ULN, or elevated total bilirubin (TBL) $\geq 2 \times$ ULN, liver tests will be performed to confirm the abnormality.

Additional safety data should be collected if 1 or more of the following conditions occur:

- elevation of ALT to $\geq 5 \times$ ULN on 2 or more consecutive blood tests
- elevated serum TBL to $\geq 2 \times$ ULN (except for cases of known Gilbert's syndrome)
- elevation of serum ALP to $\geq 2 \times$ ULN on 2 or more consecutive blood tests

The subjects' liver disease history and associated person liver disease history data will be listed. Any concomitant medication of acetaminophen/paracetamol will be listed. Results from any hepatic monitoring procedures, such as a magnetic resonance elastography (MRE) scan, and a biopsy assessment will be listed, if performed.

Hepatic risk factor assessment data will be listed. Liver related signs and symptoms data will be summarized by population and treatment, and listed. Alcohol and recreational drug use data will also be listed.

All hepatic chemistry, hematology, coagulation, and serology data will be listed. Values outside the reference ranges will be flagged on the individual subject data listings.

9.4.7 Columbia-Suicide Severity Rating Scale (C-SSRS)

Data from the C-SSRS questionnaire (suicidal ideation and behavior data, self-harm follow-up questionnaire data) will be listed for individual subjects.

9.4.8 Other assessments

Dosing details and body weight for individual subjects will be listed.

All other safety assessments not detailed in this section will be listed but not summarized or statistically analyzed.

9.4.9 Safety and Tolerability Statistical Methodology

No inferential statistical analyses are planned.

10. INTERIM ANALYSES

No interim statistical analyses are planned.

11. CHANGES FROM THE PROTOCOL SPECIFIED STATISTICAL ANALYSES

There were no changes from the protocol specified statistical analyses.

13. DATA PRESENTATION

13.1 Derived Parameters

Individual derived parameters (e.g. PK parameters) and appropriate summary statistics will be reported to three significant figures. Observed concentration data, e.g. C_{max} , should be reported as received. Observed time data, e.g. t_{max} , should be reported as received. N and percentage values should be reported as whole numbers. Median values should be treated as an observed parameter and reported to the same number of decimal places as minimum and maximum values.

13.2 Missing Data

Missing data will not be displayed in listings.

13.3 Insufficient Data for Presentation

Some of the TFLs may not have sufficient numbers of subjects or data for presentation. If this occurs, the blank TFL shell will be presented with a message printed in the centre of the table, such as, “No serious adverse events occurred for this study.”

14. REVISION OF CHANGES FROM PREVIOUS SAP VERSIONS

Version 2 of the SAP was created to include the following major changes/clarifications:

- Overall: The word “race” (Japanese, Caucasian) was replaced by “population”.
- Section. [9.4.4](#) Vital Signs: The baseline definition was clarified.
- Section. [9.4.5](#) Electrocardiogram (ECG): The baseline definition was clarified. Additionally, the example SAS code was updated so that the slope can be different for different effect group.

Leo Document ID = 51376821-27eb-4716-8423-df8b02d43af5

Approver: PPD

Approval Date & Time: 29-Aug-2018 12:28:56 GMT

Signature meaning: Approved

Approver: PPD

Approval Date & Time: 29-Aug-2018 13:09:33 GMT

Signature meaning: Approved

Approver: PPD

Approval Date & Time: 30-Aug-2018 02:25:24 GMT

Signature meaning: Approved

Approver: PPD

Approval Date & Time: 30-Aug-2018 04:33:58 GMT

Signature meaning: Approved
